3.2.1 Rationale for patient tolerability interviews

The aims of the patient tolerability interviews are to provide patient-based information regarding self-perceived side-effects of the treatment, the importance and impact on daily life of these side-effects and how they are evaluated in relation to the treatment effect. Information gained from these interviews will be used to aid in the design of future studies and programs to treat this condition.

4. PATIENT SELECTION AND RESTRICTIONS

Investigators should keep a record ie, patient screening log, of patients who entered pre-study screening.

Each patient must meet all of the inclusion criteria and none of the exclusion criteria for this study at the time of starting study treatment. Under no circumstances can there be exceptions to this rule.

4.1 Inclusion criteria

For inclusion in the study, patients must fulfil all of the following criteria.

1. Provision of signed and dated, written informed consent prior to any study specific procedures, sampling and analyses

If a patient declines to participate in any voluntary exploratory research and/or genetic component of the study, there will be no penalty or loss of benefit to the patient and he/she will not be excluded from other aspects of the study

- 2. Aged at least 18 years. Patients from Japan aged at least 20 years
- 3. Histological or cytological confirmation diagnosis of NSCLC
- 4. Radiological documentation of disease progression while on a previous continuous treatment with an EGFR TKI e.g. gefitinib or erlotinib (with the exception of 1st line expansion cohort). In addition other lines of therapy may have been given. All patients must have documented radiological progression on the last treatment administered prior to enrolling in the study.
- 5. Patients (with the exception of 1st line expansion cohort) must fulfil **one** of the following:

- Confirmation that the tumour harbours an *EGFR* mutation known to be associated with EGFR TKI sensitivity (including G719X, exon 19 deletion, L858R, L861Q)

or

- Must have experienced clinical benefit from EGFR TKI, according to the Jackman criteria^{*}(Jackman et al 2010) followed by systemic objective progression (RECIST or WHO) while on continuous treatment with EGFR TKI
- 6. For 1st Line expansion cohort ONLY, confirmation that the tumour is EGFRm^{+ve} and have had no prior therapy for their advanced disease (for 1st line patients biopsy will be at time of diagnosis of advanced disease).
- 7. **For dose expansion and extension cohorts,** patients must also have confirmation of tumour T790M mutation status (confirmed positive or negative) from a biopsy sample taken after disease progression on the most recent treatment regimen (irrespective of whether this is EGFR TKI or chemotherapy).

Prior to entry a result from the central analysis of the patient's T790M mutation status must be obtained.

- 8. World Health Organisation (WHO) performance status 0-1 with no deterioration over the previous 2 weeks and a minimum life expectancy of 12 weeks.
- 9. At least one lesion, not previously irradiated and not chosen for biopsy during the study screening period, that can be accurately measured at baseline as ≥ 10mm in the longest diameter (except lymph nodes which must have short axis ≥ 15mm) with computerised tomography (CT) or magnetic resonance imaging (MRI) which is suitable for accurate repeated measurements.
- 10. Females should be using adequate contraceptive measures (see Section 4.3), should not be breast feeding and must have a negative pregnancy test prior to start of dosing if of child-bearing potential or must have evidence of non-child-bearing potential by fulfilling one of the following criteria at screening:
 - Post-menopausal defined as aged more than 50 years and amenorrhoeic for at least 12 months following cessation of all exogenous hormonal treatments

^{*} Clinical benefit from treatment with an EGFR TKI as defined by either documented partial or complete response (RECIST or WHO) or significant and durable (≥ 6 months) clinical benefit (stable disease as defined by RECIST or WHO) after initiation of gefitinib or erlotinib. Patients with only symptomatic improvement while on EGFR TKI but no corresponding evidence of radiographic stability of disease should not be routinely considered as having sufficient clinical benefit.

- Women under 50 years old would be consider postmenopausal if they have been amenorrheic for 12 months or more following cessation of exogenous hormonal treatments and with LH and FSH levels in the post-menopausal range for the institution
- Documentation of irreversible surgical sterilisation by hysterectomy, bilateral oophorectomy or bilateral salpingectomy but not tubal ligation
- 11. Male patients should be willing to use barrier contraception ie, condoms
- 12. Patients from Japan should be willing to remain in hospital from the first dosing day until Day 1 Cycle 2
- 13. For dose expansion paired biopsy cohort:
 - Presence of at least one non-target lesion suitable for multiple biopsies on treatment
- 14. **For inclusion in optional genetic research**, patient must
 - Provide informed consent for genetic research

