The efficacy assessments of objective response (OR), duration of response (DoR), disease control rate (DCR), progression-free survival (PFS) as assessed by RECIST 1.1 and overall survival (OS) are widely accepted parameters for the assessment of efficacy for advanced NSCLC treated with EGFR TKIs (Sun et al 2010).

Preclinical data (Investigator Brochure Section 4.1.1.2) demonstrates that when the clinical efficacy in a dual mutation (L858R/T790M+) mouse xenograft model eventually develops resistance to low dose AZD9291 (1mg/kg/day) a dose escalation (to 25mg/kg/day) reverses the tumour regrowth and provides additional durable sustained tumour shrinkage. Therefore, an increase in dose of AZD9291 to a currently identified well tolerated dose (80 mg) in patients with initial objective responses but subsequent RECIST confirmed disease progression at a lower dose may have the potential to provide prolongation of the clinical benefit for these patients.

The collection of cerebrospinal fluid (CSF) will enable the investigation of the ability of AZD9291 to cross the blood brain barrier. Brain metastases occur in 20-30% of patients with advanced NSCLC, and are associated with poor prognosis (Porta 2011). The first generation EGFR TKI agents have demonstrated only limited efficacy in treating brain metastases (Bai 2013, Ranson 2013, Shimato 2006) however, preclinical data suggests that AZD9291 may be capable of crossing the blood brain barrier (Investigator Brochure) and potentially may offer better exposures in this anatomically protected location.

The collection of samples to allow investigation of the presence and/or identity of metabolites of AZD9291 and, if appropriate, characterise their pharmacokinetics will generate data to allow AstraZeneca to fulfil regulatory requirements related to the testing of the safety of metabolites.

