7.8 Description of analysis sets

The analysis of data will be based on different subsets according to the purpose of the analysis. Throughout the safety results sections, erroneously treated patients (eg, those assigned to receive dose A who actually received dose B, those who failed to meet the selection criteria) will be accounted for in the actual dose group received.

Analysis sets are presented in Table 7

Table 7Analysis sets

Analysis Set	Definition
Safety	All patients who received at least 1 dose of AZD9291.
Pharmacokinetics	Dosed patients who have at least 1 measurable plasma concentration collected post-dose.
Evaluable for response	Dosed patients with a baseline RECIST assessment.
Exploratory biomarkers	All patients that participate in the exploratory biomarker research

Analysis Set	Definition
Paired biopsy	Dosed patients with a pre-study tumour biopsy and one tumour biopsy on study treatment

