2. DEFINITION OF MEASURABLE, NON-MEASURABLE, TARGET AND NON-TARGET LESIONS

Patients with at least one lesion measurable that can be accurately assessed at baseline by computerised tomography (CT), magnetic resonance imaging (MRI) or plain X-ray should be included in this study.

Measurable lesions

At least one lesion, not previously irradiated, that can be accurately measured at baseline as \geq 10mm in the longest diameter (except lymph nodes which must have short access \geq 15mm) with computered tomography (CT) or magnetic resonance imaging (MRI) which is suitable for accurate repeated measurements.

Non-measurable lesions

- All other lesions, including small lesions (longest diameter < 10 mm or pathological lymph nodes with \geq 10 mm to < 15 mm short axis at baseline. Nodes with < 10 mm short axis are considered non-pathological and should not be recorded as non-target lesions (NTLs)
- Truly non-measurable lesions include the following: bone lesions, leptomeningeal disease, ascites, pleural / pericardial effusion, inflammatory breast disease, lymphangitic involvement of skin or lung, abdominal masses/abdominal organomegaly identified by physical examination that are not measurable by CT or MRI
- Previously irradiated lesions as localised post-radiation changes, which affect lesion sizes, may occur. Therefore, lesions that have been previously irradiated will not be considered measurable and should be selected as NTLs at baseline and followed up as part of the NTL assessment
- Skin lesions assessed by clinical examination
- Brain metastasis

Clinical Study Protocol Appendix F Drug Substance AZD9291 Study Code D5160C00001 Edition Number 1 Date

Special cases

- Lytic bone lesions or mixed lytic–blastic lesions, with identifiable soft tissue components, can be considered measurable if the soft tissue component meets the definition of measurability. Blastic lesions are considered non-measurable.
- Cystic metastases can be considered measurable lesions if they meet the criteria for measurability from a radiological point of view, but if non-cystic lesions are present in the same patient, these non-cystic lesions should be selected as the target lesions (TLs).

Target lesions

A maximum of 5 measurable lesions (with a maximum of 2 lesions per organ), representative of all lesions involved suitable for accurate repeated measurement, should be identified as TLs at baseline.

Non-target lesions

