4.2 Target lesions

4.2.1 Documentation of target lesions

A maximum of 5 measurable lesions, with a maximum of 2 lesions per organ (including lymph nodes), representative of all lesions involved, should be identified as TLs at baseline. Target lesions should be selected on the basis of their size (longest diameter for non-nodal lesions or short axis for nodal lesions) but in addition should be those that lend themselves to reproducible repeated measurements. It may be the case that, on occasion, the largest lesion does not lend itself to reproducible measurement in which circumstance the next largest lesion, which can be measured reproducibly, should be selected.

The site and location of each TL should be documented as well as the longest diameter for non-nodal lesions (or short axis for lymph nodes). All measurements should be recorded in millimetres. At baseline, the sum of the diameters for all TLs will be calculated and reported as the baseline sum of diameters. At follow-up visits the sum of diameters for all TLs will be calculated and reported as the follow-up sum of diameters.

Special cases:

- For TLs measurable in 2 or 3 dimensions, always report the longest diameter. For pathological lymph nodes measurable in 2 or 3 dimensions, always report the short axis.
- If the CT/MRI slice thickness used is > 5mm, the minimum size of measurable disease at baseline should be twice the slice thickness of the baseline scan.
- If a lesion has completely disappeared, the longest diameter should be recorded as 0 mm.
- If a TL splits into two or more parts, then record the sum of the diameters of those parts

- If two or more TLs merge then the sum of the diameters of the combined lesion should be recorded for one of the lesions and 0 mm recorded for the other lesion(s)
- If a TL is believed to be present and is faintly seen but too small to measure, a default value of 5 mm should be assigned. If an accurate measure can be given, this should be recorded, even if it is below 5mm.
- If a TL cannot be measured accurately due to it being too large, provide an estimate of the size of the lesion
- When a TL has had any intervention eg, radiotherapy, embolisation, surgery etc, during the study, the size of the TL should still be provided where possible

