4.6 Evaluation of Overall Visit Response

Table 4 Over all visit Response			
Target lesions	Non-Target lesions	New Lesions	Overall response
CR	CR	No	CR
CR	NA	No	CR
CR	Non-CR/Non PD	No	PR
CR	NE	No	PR
PR	Non PD or NE	No	PR
SD	Non PD or NE	No	SD
NA	Non CR/Non PD	No	SD (Non CR/non PD)
NE	Non-PD or NE	No	NE
NA	NE	No	NE
PD	Any	Yes or No	PD
Any	PD	Yes or No	PD
Any	Any	Yes	PD

The overall visit response will be derived using the algorithm shown in Table 4.

Overall Visit Response

CR = complete response, PR = partial response, SD = stable disease, PD = progressive disease

IR = incomplete response, NE = not evaluable, NA = not applicable (relevant when no NTLs at baseline)

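### Inclusion criterion 9 does not require a lesion that is measurable under Appendix F, and the escalation and expansion response set does not make up for it

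*Protocol*

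**What the plan says.** **Entry.** Section 4.1, criterion 9, requires at least one lesion, not irradiated and not chosen for the screening biopsy, "that can be accurately measured at baseline as ≥ 10mm in the longest diameter" (nodes 15 mm in short axis) by CT or MRI and "which is suitable for accurate repeated measurements". It names no anatomical site, sets no slice-thickness condition and does not cite Appendix F. Section 4.2, exclusion 3, lets in patients with stable, asymptomatic brain metastases that have not needed steroids for 4 weeks. It does not require that they have been irradiated.

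**Scoring.** Appendix F, section 2, repeats nearly the same size rule for measurable lesions, without the biopsy clause. It then lists "Brain metastasis" among the non-measurable lesions. Appendix F, section 4.2.1, adds that on slices thicker than 5 mm "the minimum size of measurable disease at baseline should be twice the slice thickness of the baseline scan", and Appendix F, section 5.1, expects such slices at some institutions as an exception. Target lesions are chosen from measurable lesions only. In Appendix F Table 4 (section 4.6), a partial response arises only through a complete or partial response of target lesions. With no target lesions and persisting non-target disease, the result is "SD (Non CR/non PD").

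**Analysis sets.** Table 7 (Section 7.8) defines the set evaluable for response as "Dosed patients with a baseline RECIST assessment", and Section 7.2.2 uses the same condition for expansion. For the extension, Sections 7.7.1 and 7.9 limit ORR to patients with measurable disease, as judged by independent central review (ICR) for the primary analysis. Section 7.1 makes ORR primary in the extension and secondary in escalation and expansion.

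**The concern.** The rule that admits patients is wider than the rule that decides whether they can be scored as responders. Two kinds of lesion pass the first and fail the second: an unirradiated brain metastasis of at least 10 mm, and a lesion of about 10 mm seen on slices above 5 mm. A patient with nothing else measurable would be treated and assessed, and could never reach a partial response.

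What follows depends on the cohort. In escalation and expansion nothing takes this patient out of the denominator, so the observed ORR is pulled down for a reason unrelated to the drug. Section 7.2.2.1 uses responses to judge whether there is any activity and allows a cohort to close early after no responses in 8 patients. That rule carries a stated error risk, and the risk assumes that every one of the 8 is able to respond.

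**Working it through.** **Step 1: the rules side by side.**

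| Lesion | Criterion 9 | Appendix F |
|---|---|---|
| Brain metastasis, 10 mm or more, unirradiated, on MRI | Met, if repeat measurement is feasible | Non-measurable (section 2) |
| 10 mm lesion on 8 mm slices (illustrative) | Met, if repeat measurement is feasible | Non-measurable: needs 2 x 8 = 16 mm (section 4.2.1) |

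**Step 2: is the no-target-lesion case foreseen?** Yes. Appendix F Table 3 has a note for patients without target lesions, and Table 4 has rows for that state. Section 7.9 restricts the tumour-size analysis to evaluable patients who have measurable disease, which implies that some evaluable patients may not. Table 4 has no row for absent target lesions together with complete disappearance of non-target lesions, so a complete response in such a patient is undefined.

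**Step 3: reproduce the plan's figures (Section 7.2.2.1).** The chance of no responses among n patients at true rate p is (1 - p)^n. With p = 0.30:
- n = 8: 0.70^8 = 5.76%, stated as below 6%. Reproduced.
- n = 30: 0.70^30 = 0.002%, stated as below 1%. Reproduced.

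**Step 4: expansion, with k patients who cannot score a response.** The number affected is not in the protocol, so k is an assumption. It is also assumed that none of them is scored as a complete response.

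Chance of no responses in 8 = 0.70^(8 - k):
- k = 1: 0.70^7 = 8.2%
- k = 2: 0.70^6 = 11.8%
- k = 3: 0.70^5 = 16.8%

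One in 8 is a larger share than 1 to 3 in 30. If instead each patient independently has a 1/30, 2/30 or 3/30 chance of being affected, the effective response rate is 0.30 x 29/30 = 0.29, then 0.28, then 0.27. The risk is 0.71^8 = 6.5%, 0.72^8 = 7.2% and 0.73^8 = 8.1%, already above the stated 6% at the smallest share.

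Expected ORR in 30 = true ORR x (30 - k)/30. At a true 50%: 48.3% (k = 1), 46.7% (k = 2), 45.0% (k = 3). The full-cohort rule is not at risk: with k = 3, 0.70^27 = 0.007%.

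**Step 5: extension.** Affected patients leave the ORR denominator, so the estimate is not diluted. Assuming 0%, 2%, 5% or 10% without ICR-measurable disease, n is 175, 172, 166 or 158. The largest Clopper-Pearson 95% half-width, at an ORR near 50%, is 7.6, 7.7, 7.9 or 8.1 points. Section 7.2.4 states within 8 points.

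**The case against.** Several points on the other side stand.

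- **The rules are not opposed.** Appendix F's paragraph on measurable lesions is close to criterion 9, and its section 2 says that patients with a measurable lesion should be included. Section 6.10.1 sends the reader to Appendix F. A careful site reading both would keep most such patients out. This makes the defect a missing cross-reference, but it does not remove it, because Section 4 binds sites to the criteria as written.
- **The repeat-measurement wording may screen out some thick-slice cases.** It leaves that to judgement, and Appendix F treats thick slices as exceptional. The brain case is untouched.
- **The effect on expansion ORR is modest.** A shift of 1.7 to 5 points at 50% lies well inside the 80% interval of 37% to 63% that Section 7.2.2.1 accepts for a preliminary, secondary estimate. That is fair for the full cohort, less so for closure after 8 patients.

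A reader might also infer more than the documents support:

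- **That the mandatory T790M biopsy leaves a patient with one other lesion, in the brain, without a target lesion.** Only criterion 9 bars the biopsied lesion. Appendix F does not, and Section 7.7 sends biopsy reports to the ICR without a ban. If the biopsied lesion is measurable it can be a target lesion. The problem needs that lesion to be non-measurable too.
- **That such a patient is bound to be a non-responder.** A partial response is unavailable, but a complete response from non-target lesions alone is left undefined in Table 4, not ruled out.
- **That the plain X-ray phrase in Appendix F, "magnetic resonance imaging (MRI) or plain X-ray should be included in this study", admits further patients.** It admits nobody, because criterion 9 must also be met and requires CT or MRI.
- **That the primary ORR in the extension is biased.** Sections 7.7.1 and 7.9 already restrict it to measurable disease.

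**Conclusion.** The point holds as a gap between the entry rule and the scoring rule, with a real but probably small effect in the cohorts that lack a measurable-disease condition. It concerns only patients with no lesion measurable under Appendix F. The protocol gives no frequency for them. Its statement "Brain metastases occur in 20-30% of patients with advanced NSCLC" covers brain metastases of any kind and cannot be used as that share.

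The most sensitive place is early closure of an expansion cohort, where the stated risk has almost no margin (5.76% against 6%) and one affected patient among 8 takes it to 8.2%. In the extension the only cost is patients treated without contributing to the primary estimate. Precision stays within the stated 8 points at losses of 2% to 5% and exceeds it by about a tenth of a point at 10%. All these sizes rest on assumed counts. The change is worth making because it aligns two rules already in the protocol and costs little, not because a large bias has been shown.

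**What to change.** 1. In criterion 9, require at least one lesion that is measurable as defined in Appendix F and is neither previously irradiated nor chosen for biopsy. Say explicitly that a brain metastasis does not qualify and that on slices above 5 mm the lesion must be at least twice the slice thickness.
2. In Section 7.2.2 and Table 7, add measurable disease at baseline to the response set for escalation and expansion, as the extension already does for ORR.
3. As tidying only, delete the reference to plain X-ray from the opening sentence of Appendix F, section 2, since the methods table there does not allow it for target lesions.

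The cost is a few wording changes and possibly a few more screen failures. With every counted patient able to be scored as a responder, the stated risk of below 6% for no responses in 8 holds again.

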4.2 Exclusion criteria

Patients must not enter the study if any of the following exclusion criteria are fulfilled

- 1. Treatment with any of the following:
 - Treatment with an EGFR TKI (eg, erlotinib or gefitinib) within 8 days or approximately 5x half-life, whichever is the longer, of the first dose of study treatment. (If sufficient wash-out time has not occurred due to schedule or PK properties, an alternative appropriate wash-out time based on known duration and time to reversibility of drug related adverse events could be agreed upon by AstraZeneca and the Investigator)
 - Any cytotoxic chemotherapy, investigational agents or anticancer drugs for the treatment of advanced NSCLC from a previous treatment regimen or clinical study within 14 days of the first dose of study treatment.
 - AZD9291 in the present study (ie, dosing with AZD9291 previously initiated in this study)
 - Major surgery (excluding placement of vascular access) within 4 weeks of the first dose of study treatment
 - Radiotherapy with a limited field of radiation for palliation within 1 week of the first dose of study treatment, with the exception of patients receiving radiation to

more than 30% of the bone marrow or with a wide field of radiation which must be completed within 4 weeks of the first dose of study treatment

- Patients currently receiving (or unable to stop use at least 1 week prior to receiving the first dose of AZD9291) medications or herbal supplements known to be potent inhibitors of CYP2C8 and potent inhibitors or inducers of CYP3A4 (Appendix H)
- 2. Any unresolved toxicities from prior therapy greater than Common Terminology Criteria for Adverse Events (CTCAE) grade 1 at the time of starting study treatment with the exception of alopecia and grade 2, prior platinum-therapy related neuropathy
- 3. Spinal cord compression or brain metastases unless asymptomatic, stable and not requiring steroids for at least 4 weeks prior to start of study treatment
- 4. Any evidence of severe or uncontrolled systemic diseases, including uncontrolled hypertension and active bleeding diatheses, which in the investigator's opinion makes it undesirable for the patient to participate in the trial or which would jeopardise compliance with the protocol, or active infection including hepatitis B, hepatitis C and human immunodeficiency virus (HIV). Screening for chronic conditions is not required
- 5. Any of the following cardiac criteria:
 - Mean resting corrected QT interval (QTc) > 470 msec obtained from 3 electrocardiograms (ECGs), using the screening clinic ECG machine derived QTc value
 - Any clinically important abnormalities in rhythm, conduction or morphology of resting ECG eg, complete left bundle branch block, third degree heart block, second degree heart block, PR interval >250msec
 - Any factors that increase the risk of QTc prolongation or risk of arrhythmic events such as heart failure, hypokalaemia, congenital long QT syndrome, family history of long QT syndrome or unexplained sudden death under 40 years of age in first degree relatives or any concomitant medication known to prolong the QT interval
- 6. Past medical history of interstitial lung disease, drug-induced interstitial lung disease, radiation pneumonitis which required steroid treatment, or any evidence of clinically active interstitial lung disease
- 7. Inadequate bone marrow reserve or organ function as demonstrated by any of the following laboratory values:
 - Absolute neutrophil count $< 1.5 \times 10^9/L$

- Platelet count $< 100 \text{ x } 10^9/\text{L}$
- Haemoglobin < 90 g/L
- Alanine aminotransferase > 2.5 times the upper limit of normal (ULN) if no demonstrable liver metastases or > 5 times ULN in the presence of liver metastases
- Aspartate aminotransferase > 2.5 times ULN if no demonstrable liver metastases or > 5 times ULN in the presence of liver metastases
- Total bilirubin > 1.5 times ULN if no liver metastases or > 3 times ULN in the presence of documented Gilbert's Syndrome (unconjugated hyperbilirubinaemia) or liver metastases
- Creatinine >1.5 times ULN concurrent with creatinine clearance < 50 ml/min (measured or calculated by Cockcroft and Gault equation); confirmation of creatinine clearance is only required when creatinine is > 1.5 times ULN
- 8. Refractory nausea and vomiting, chronic gastrointestinal diseases, inability to swallow the formulated product or previous significant bowel resection that would preclude adequate absorption of AZD9291
- 9. History of hypersensitivity to active or inactive excipients of AZD9291 or drugs with a similar chemical structure or class to AZD9291
- 10. Women who are breast feeding
- 11. Involvement in the planning and conduct of the study (applies to AstraZeneca staff or staff at the study site)
- 12. Judgment by the investigator that the patient should not participate in the study if the patient is unlikely to comply with study procedures, restrictions and requirements

In addition, the following is considered a criterion for exclusion from the exploratory genetic research:

- 13. Previous allogenic bone marrow transplant
- 14. Non-leukocyte depleted whole blood transfusion within 120 days of the date of the genetic sample collection

4.3 **Restrictions**

The following restrictions apply while the patient is receiving study treatment and for the specified times before and after:

- 1. Females of child-bearing potential should use reliable methods of contraception from the time of screening until *3 months* after discontinuing study treatment. Acceptable methods of contraception include abstinence, tubal ligation, oral or transdermal contraceptives, copper-banded intra-uterine devices and vasectomised partner. All hormonal methods of contraception should be used in combination with the use of a condom by their male sexual partner for intercourse.
- 2. Male patients should be asked to-use barrier contraceptives (ie, by use of condoms) during sex with all partners during the trial and for a washout period of 3 months. Patients should avoid procreation for *6 months* after completion of trial treatment. Patients should refrain from donating sperm from the start of dosing until *6 months* after discontinuing study treatment. If male patients wish to father children they should be advised to arrange for freezing of sperm samples prior to the start of study treatment.
- 3. All patients must try to avoid concomitant use of medications, herbal supplements and/or ingestion of foods with known potent inducer/inhibitory effects on CYP3A4 and/ or CYP2C8 whenever feasible, but patients may receive any medication that is clinically indicated for treatment of adverse events. Such drugs must have been discontinued for an appropriate period before they enter screening and for a period of *3 months* after the last dose of AZD9291. All concomitant medications should be captured on the eCRF. Guidance on medicines to avoid, medications that require close monitoring and on washout periods is to be provided.
- 4. Patients who wear contact lenses must discontinue wearing their lenses if they have any mild to moderate eye symptoms (CTCAE grade ≤2) while receiving treatment with AZD9291 until at least one week after symptoms have resolved. If a patient has a recurrence of eye symptoms or experiences any severe (CTCAE grade ≥3) ocular events they must discontinue wearing their contact lenses until at least one week after treatment with AZD9291 is permanently discontinued. Patients must not use any eye drops or ointment for treatment of eye symptoms, unless agreed by a study doctor, at any time during the study until 1 week after AZD9291 has been permanently discontinued. Patient should consult the clinic promptly if they have any concerns.

For restrictions relating to concomitant medications see next Section 4.3.1.

